7. RATIONALE AND BACKGROUND

The term interstitial lung disease (ILD) encompasses a large group of over 200 pulmonary disorders. While idiopathic pulmonary fibrosis (IPF) is the best-known progressive fibrosing ILD (PF-ILD), there is a group of patients with different underlying clinical ILD diagnoses other than IPF who develop a progressive fibrosing phenotype during the course of their disease (e.g., idiopathic interstitial pneumonias [IIPs] such as idiopathic nonspecific interstitial pneumonia [iNSIP] and unclassifiable IIP; hypersensitivity pneumonitis [HP]; autoimmune interstitial lung disease [connective tissue disease-ILDs (CTD-ILD) such as rheumatoid arthritis-ILD (RA-ILD), systemic sclerosis-ILD (SSc-ILD) and anti-synthetase syndrome]; Sarcoidosis; Pneumoconiosis/exposure related ILD) [P17-10582, P18-04729, P19-01738, R19-0854]. These patients demonstrate a number of similarities to patients with IPF, with their disease being defined by the presence of progressive pulmonary fibrosis, worsening respiratory symptoms, declining lung function despite immunomodulatory therapies and, ultimately, early mortality.

Although there had been no indicated therapies for patients with chronic fibrosing ILDs with a progressive phenotype (other than IPF), Nintedanib has just been approved for SSc-ILD in the end of Dec. 2019 based on the results of the SENSCIS trial (NCT02597933) [P19-04387] and for PF-ILDs in the end of May 2020 in Japan based on the results of the INBUILD trial (NCT02999178) [P19-08802, P20-02333].

There is minimal literature available to estimate the proportion of patients who develop PF-ILDs in patients with fibrosing ILD other than IPF in Japan. In addition, the current management and treatment for these diseases are not well-known. These information are keys to gaining a better understanding of the size of this population with high unmet need and for physicians, patients and other stakeholders to optimize allocation of resources, diagnostic assessment and management of this patient population.

Therefore, this study will use the database from Medical Data Vision (MDV) to investigate the incidence probability of progression to PF-ILDs according to each co-existing underlying diseases and the characteristics of procedures for management and treatment in patients with fibrosing ILD other than IPF.

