9. RESEARCH METHODS

9.1 STUDY DESIGN

This is a retrospective cohort study using the database from MDV.

Data from 01-Jan-2012 to 28-May-2020 will be used. It will be considered that each patient is observable from his/her first encounter to his/her last encounter in the database. The patients with fibrosing ILD will be identified in the period from 01-Jan-2013 to 6 months before 28-May-2020. Each patient who meets all the inclusion criteria and none of the exclusion criteria will be followed up from the day after the index date* until the end of study period (i.e. 28-May-2020), the last encounter in the MDV database, in-hospital death, whichever occurs first.

*The index date will be the date of the second diagnosis of fibrosing ILD. Please refer to the Section 9.2.2.1 for the detailed codes of fibrosing ILD.

*The index date will depend on the time the patient fulfils the eligibility criteria

Figure 1 . Schematic of the Study Design

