9.3 VARIABLES

9.3.1 Outcomes

9.3.1.1 Primary outcome

Incidence probability of progression to PF-ILDs at 6, 12, 18, and 24 months after the index date*

Progression to PF-ILD as event in this study is defined in Table 1 as well as Annex 2. Event date will be the date when the one of criteria of the progression to PF-ILD is met.

*The index date will be the date of the second diagnosis of fibrosing ILD. Please refer to the Section 9.2.2.1 for the detailed codes of fibrosing ILD.

Table 1. Interstitial lung disease progression proxies

Proxy
- ≥ 3 pulmonary function tests on different dates of service within 365 days - The date of the 3 rd pulmonary function test will be the date of progression
- ≥ 3 HRCT/CT on different dates of service within 365 days - The date of the 3 rd HRCT/CT will be the date of progression
≥ 1 claim for oxygen therapy (HOT) during follow-up period
≥ 1 respiratory hospitalization during follow-up period
≥ 1 claim for palliative care during follow-up period
≥ 1 lung transplant during follow-up period
≥ 1 new* claim for immunosuppressive drugs during follow-up period with at least two out of the three test codes** within 3 months before new claims for immunosuppressive drugs Rituximab Tacrolimus Mycophenolate Cyclosporine Cyclophosphamide Azathioprine Tocilizumab
*: Not received in the 12 months prior to the index date **: ① Pulmonary function tests, ② HRCT/CT, ③ KL-6 or SP-D
≥ 1 new* claim for oral corticosteroid with a prednisone-equivalent dose of >20 mg during follow-up period and with at least two out of the three test codes* within 3 months before new claims for oral corticosteroid *: Not received in the 12 months prior to the index date **: ① Pulmonary function tests, ② HRCT/CT, ③ KL-6 or SP-D
≥ 1 claim for Nintedanib* during follow-up period *: Patients meeting this criterion will be counted only if patients with fibrosing ILDs meet this criterion on or after 29-May-2020, because nintedanib was approved for PF-ILD on 29-May-2020. Even if patients with fibrosing ILDs meet this criterion on or before 28-May-2020, they will not be counted.

HRCT; high-resolution computed tomography, CT; computed tomography, KL-6; krebs von den lungen-6, SP-D; surfactant protein D

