9.7.4 Sensitivity analysis

- 1) The end of data extraction period will be changed from 28-May-2020 to the latest data cut off. OFEV was approved for PF-ILD on 29-May-2020, and the characteristics of claims data before and after the above approval for new indications might not be different. To increase the sample size, all the analyses will be repeated with this data extraction period.
- 2) The index date will be changed from the date of the second code of fibrosing ILD to the date of the first code of fibrosing ILD because there might be patients who are asked to visit hospitals annually after the first diagnosis. All the analyses will be repeated with this index date.

In addition, all the analyses will be repeated with both data extraction period and index date changed.

After exploring the proxy patterns among patients meeting the criteria of progression to PF-ILD as described in Section 9.7.2.2, a sensitivity analysis with modified progression criteria might be performed.

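### Sensitivity analysis 1 and the combined analysis switch on a ninth progression proxy (any nintedanib claim from 29-May-2020, SSc-ILD use included), so they test more than the data cut-off

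*Combined protocol and SAP*

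**What the plan says.** Section 9.1 fixes the main data window, "Data from 01-Jan-2012 to 28-May-2020 will be used", and follows each patient "until the end of study period (i.e. 28-May-2020), the last encounter in the MDV database, in-hospital death, whichever occurs first".

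Table 1 in 9.3.1.1 lists nine progression proxies. The ninth is "≥ 1 claim for Nintedanib* during follow-up period", with a footnote that opens the counting window one day after the main data end: "Patients meeting this criterion will be counted only if patients with fibrosing ILDs meet this criterion on or after 29-May-2020". The footnote gives the PF-ILD approval on that date as the reason and adds: "Even if patients with fibrosing ILDs meet this criterion on or before 28-May-2020, they will not be counted". Annex 2 repeats the row and identifies the drug by generic name and ATC codes only.

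The immunosuppressant row is stricter: "≥ 1 new* claim for immunosuppressive drugs during follow-up period with at least two out of the three test codes". The oral corticosteroid row has the same two conditions.

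Section 9.7.4 moves the data end to the latest cut-off in sensitivity analysis 1, repeats all analyses, and names a larger sample as the aim. Its justification is that "the characteristics of claims data before and after the above approval for new indications might not be different". A further run changes both the data end and the index date. Section 7 states: "Nintedanib has just been approved for SSc-ILD in the end of Dec. 2019". SSc-ILD patients are eligible (9.2.2.1) and are a reported subgroup for the primary outcome (9.7.3).

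**The concern.** A sensitivity analysis on the data cut-off should hold the event definition still. Here the written list of proxies is the same in both analyses, but the set that can produce an event is not, and section 9.7.4 does not mention this. If the cumulative incidence moves, the reader cannot tell whether longer data or the added event type moved it.

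The date gate also rests on the idea that a nintedanib claim after PF-ILD approval signals PF-ILD. For SSc-ILD that does not follow, because the drug already had its own approval for that disease. Indicated treatment of SSc-ILD would be recorded as progression in a subgroup estimate that the study intends to report.

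Section 9.9 acknowledges that the claims algorithm is unvalidated and relies on sensitivity analysis to judge robustness, so these runs need to be interpretable.

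**Working it through.** The plan states no figure to reproduce: there is no sample-size calculation and no expected incidence. The check is of dates and wording.

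**1. Overlap in the main analysis.** Follow-up closes 28-May-2020 (9.1) and the row opens 29-May-2020 (Table 1). Overlap: 0 days. Eight of nine proxies can operate in the main analysis, and nine of nine in sensitivity analysis 1 and the combined analysis.

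**2. SSc-ILD.** Taking the end of December 2019 as 31-Dec-2019 (an assumption about the day), SSc-ILD approval precedes the opening of the row by 150 days. Two cases follow.
- First nintedanib claim on or after 29-May-2020 for SSc-ILD: counted as progression on any reading of the row.
- First nintedanib claim within those 150 days, with claims continuing after 28-May-2020: unclear. If the last sentence of the footnote discards claims, the next claim from 29-May-2020 is an event. If it discards patients, the patient never counts under this row.

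**3. Who can be affected at each time point.** A claim changes the estimate at a given month only if it falls within that many months of index. Suppose the identification period stays as in 9.2.2.1, taken as 01-Jan-2013 to 28-Nov-2019 (2,523 days), with index dates spread evenly (assumed).
- 6 months: the latest index date plus 6 months is 28-May-2020, so no patient.
- 12 months: index from 29-May-2019, 184 days; 184/2,523 = 7%.
- 18 months: index from 29-Nov-2018, 365 days; 365/2,523 = 14%.
- 24 months: index from 29-May-2018, 549 days; 549/2,523 = 22%.

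If identification also moves later, these shares rise, but the new cut-off is not given.

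**4. Form of the effect.** Let p be the cumulative incidence from the other eight proxies at the horizon, and f the share of patients still event-free on those proxies who have a counted nintedanib claim within the horizon. Added incidence = (1 − p) × f. Neither input is in the documents. For assumed f of 0.05 to 0.20 in SSc-ILD:
- p = 0.30: 0.70 × f = 3.5 to 14.0 percentage points
- p = 0.50: 0.50 × f = 2.5 to 10.0 points
- p = 0.70: 0.30 × f = 1.5 to 6.0 points

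With identification fixed and even accrual, step 3 limits f at 24 months to about 0.22, and reaching that would need a timely claim from every patient whose horizon extends past 28-May-2020. These are illustrations, not estimates.

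**The case against.** The strongest reply is that the gate is deliberate. The protocol states the rule and its reason, and the row exists for the extended data. That stands: a reader might infer that an inert row makes the main analysis defective, but the documents do not support this, and the primary estimate is not biased by it.

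Three other inferences go too far.
- That refills by patients who started before 29-May-2020 certainly become events, with dates clustering just after it. This needs the claim-level reading of the footnote; its grammatical subject is patients, which supports the other reading.
- That SSc-ILD patients with a claim in baseline are removed by exclusion criterion 2. Section 9.7.4 moves the data extraction end and does not say that identification moves. If it stays fixed, no baseline period reaches 29-May-2020. The aim of a larger sample suggests that it might move, but no more than that.
- That the 24-month SSc-ILD estimate rises by a stated amount, for example by applying the share of patients with any later claim. This ignores the horizon limit in step 3 of the working.

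It can also be said that the contribution will be visible: 9.7.2.2 tabulates the criteria met among progressors, 9.7.3 repeats the analyses by subgroup, and 9.7.4 allows for modified criteria. This helps only in part. The tabulation neither isolates patients whose sole event is nintedanib nor gives a Kaplan-Meier estimate without the row, and the modified-criteria analysis is optional.

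Finally, disabling the proxy for SSc-ILD alone would give that subgroup a different endpoint from the others. That is fair, and it argues for a reported variant rather than a sole rule.

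**Conclusion.** The point holds for sensitivity analysis 1 and the combined analysis only. In both, the operative event set goes from eight proxies to nine at the same time as the data end moves, so a difference from the main result has no single explanation. That rests on stated dates and needs no assumption. It is equally firm that a first nintedanib claim for SSc-ILD from 29-May-2020 counts as PF-ILD progression, since the row has no indication condition. Whether continuing claims count is unclear and should be settled in the text. The size cannot be derived from the documents. It depends on how many patients have no event under the other eight proxies, on nintedanib use, and on whether identification moves. This is a cheap improvement to the sensitivity analyses, not a flaw in the primary estimate.

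**What to change.** In 9.7.4, specify that sensitivity analysis 1 and the combined analysis are run first with the same eight proxies as the main analysis (nintedanib row off), then with the row on as a second line. The first line isolates the change of data; the second shows what the row adds.

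For the second line, amend the row in Table 1 and Annex 2 to count only a patient's first nintedanib claim, with none in the 12 months before that claim. This settles the footnote's ambiguity. The look-back should run from the claim. The 12 months before index used in the neighbouring rows would miss a patient indexed in 2019 who started in early 2020 and continued.

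Report the overall estimate and the SSc-ILD subgroup estimate with and without nintedanib-only events in SSc-ILD patients. State whether the identification period moves in these analyses; if it does, apply the same first-claim rule to exclusion criterion 2.

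The cost is some wording, one repeated program run and an extra set of tables.

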9.2.2 Study population

9.2.2.1 Eligibility criteria

Patients who meet all of the inclusion criteria and do not meet any of the exclusion criteria will be included in the study population.

Inclusion Criteria:

- 1) Patients diagnosed with at least two fibrosing ILD codes^{*1} on different dates in the patient identification period from 01-Jan-2013 to 6 months before 28-May-2020
- 2) Patients aged 18 years and older on the index date
- 3) Patients for whom data for the 12 months prior to the index date can be extracted as baseline data

*1 International Statistical Classification of Diseases and Related Health Problems (ICD-10) code or disease code: J84.1, J84.9, 8844510, 8848382, 8844341, 8848278, 8836513, 8848267, 8848302, 8839362, 8848283, 8837013, 8834158, 8848245, 8840951, 8847737

Exclusion Criteria:

- 1) Patients grouped into the underlying disease of IPF^{*1}
- 2) Patients who have met PF-ILD progression criteria during the baseline period

*1 Please refer to the ANNEX 5 for algorithm to define underlying diseases

Note: only diagnosis records without 'suspect flag' are to be considered for evaluating diagnosis related in/excl criteria"

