9.3.2 Covariates

The following information will be extracted from MDV in this study.

Table 2. Definition of variables

Variable	Data extraction period	Details
Sex	Index date	Male/Female
Age	Index date	Age at Index date
Comorbidity and medical history	12 months before the index date (included)	
 - Coronary heart disease - Gastro-esophageal reflux disease - Obstructive sleep apnoea syndrome - Chronic obstructive pulmonary disease (COPD) - Lung cancer - Pulmonary hypertension 
See Annex 4 for code to define each comorbidity and medical history

Underlying disease (Pre-specified ILD)	12 months before the index date (included)	
 - Underlying Autoimmune Disease (Autoimmune ILD, Non-autoimmune ILD, Multiple, Unknown) - ILD Category (Hypersensitive pneumonitis, Exposure-related ILD, idiopathic nonspecific interstitial pneumonia (iNSIP), Unclassifiable idiopathic interstitial pneumonias (IIP), Sarcoidosis, RA-ILD, SSc-ILD, mixed connective tissue disease-ILD (MCTD-ILD), Other autoimmune ILD, Other ILD, Multiple, Unknown) - Pre-Specified ILD Clinical Diagnosis (Hypersensitive pneumonitis, Exposure-related ILD, iNSIP, Unclassifiable IIP, Sarcoidosis, RA-ILD, SSc-ILD, MCTD-ILD, Systemic Lupus Erythematosus-ILD (SLE-ILD), Polymyositis/Dermatomyositis-ILD (PM/DM-ILD), Sjogren ILD, Other autoimmune ILD, Other ILD, Multiple, Unknown) 
See Annex 5 for algorithm to define underlying diseases

Treatment	6 months before the index date (included) Follow-up period	
 - Rituximab - Tacrolimus - Mycophenolate - Cyclosporine - Cyclophosphamide - Azathioprine - Oral Corticosteroid - Tocilizumab - Nintedanib 
See Annex 3 for code to define each treatment
 
As for corticosteroid and immunosuppressive drugs during follow-up period, the same condition used for criteria of progression to PF-ILD will be applied.

Management	Follow-up period	
 - Oxygen therapy (HOT) - Lung transplant - Palliative care (oxygen inhalation, opioid use) 
See Annex 3 for code to define each management

Clinical examination	6 months before the index date (included)	
 - Pulmonary function test - HRCT/CT - KL-6 - SP-D 
See Annex 3 for code to define each clinical examination

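### A baseline nintedanib claim triggers neither exclusion, so the primary risk set can contain prior users; a committed sensitivity analysis without them is missing

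*Combined protocol and SAP*

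**What the plan says.** **Dates.** Under Section 9.1, "The patients with fibrosing ILD will be identified in the period from 01-Jan-2013 to 6 months before 28-May-2020", and "The index date will be the date of the second diagnosis of fibrosing ILD". Section 9.2.2.1 requires 12 months of baseline data. Follow-up starts the day after the index date and ends no later than 28-May-2020.

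**Exclusions.** Section 9.2.2.1 has two. The first is "Patients grouped into the underlying disease of IPF", decided by the Annex 5 algorithm. The second is "Patients who have met PF-ILD progression criteria during the baseline period".

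**The nintedanib criterion.** Table 1 and Annex 2 list a nintedanib claim as a progression proxy, but only from 29-May-2020, the date given for the PF-ILD approval. For earlier claims: "Even if patients with fibrosing ILDs meet this criterion on or before 28-May-2020, they will not be counted". The immunosuppressant and oral corticosteroid rows require a new claim, with no receipt in the year before index. The nintedanib row has no such condition.

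**Indications.** Section 7 says "there had been no indicated therapies for patients with chronic fibrosing ILDs with a progressive phenotype (other than IPF"), and then names two approvals: SSc-ILD at the end of December 2019 and PF-ILD at the end of May 2020.

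**Use of baseline nintedanib.** Table 2 lists it among treatments, with the windows "6 months before the index date (included) Follow-up period". Section 9.7.2.1 describes baseline treatment overall and by progression status, and Section 9.7.3 repeats this by underlying disease. No eligibility rule mentions the drug, and no planned estimate of the primary outcome uses it.

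**The concern.** The primary outcome is progression in patients who do not have IPF and have not already met the progression criteria. A patient already taking nintedanib at a time when the plan names no non-IPF indication may not belong to that population: the claim may reflect treatment as IPF, or use for a fibrosing ILD that the treating physician already considered progressive. The rule on pre-approval claims is explained as a rule about events. Because exclusion 2 borrows the same criteria, the rule also stops the claim from acting at baseline, and the plan does not discuss that side effect.

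At stake are the Kaplan-Meier estimates at 6, 12, 18 and 24 months, overall and in any subgroup where such patients gather. In the analysis to the latest cut-off there is a second consequence: a refill by a prior user on or after 29-May-2020 could be dated as new progression.

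**Working it through.** **1. Dates (Sections 7, 9.1 and 9.3.1.1).**
- 28-May-2020 minus 6 months = 28-Nov-2019. This is the latest index date and so the latest baseline claim.
- To the SSc-ILD approval, reading the end of December 2019 as 20 to 31 December: 22 to 33 days later.
- To 29-May-2020: 2 + 31 + 31 + 29 + 31 + 30 + 29 = 183 days later.

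Every baseline nintedanib claim in the main analysis therefore precedes both named approvals. Moving the index to the first code (sensitivity analysis 2) only makes it earlier.

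**2. Exclusion 2.** A claim no later than 28-Nov-2019 falls under the date limit of the row, so it cannot meet that criterion at baseline. Nor can the row produce an event in the main analysis, because follow-up ends one day before counting starts.

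**3. Exclusion 1.** Annex 5 uses diagnosis codes on the index date and underlying-disease codes in the lookback; drug claims play no part. Applying its steps to test cases:

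| Codes | Annex 5 group | Result |
|---|---|---|
| IPF code alone on the index date, no underlying-disease code | IPF | Excluded |
| IPF code only on the earlier date, J84.9 on the index date | Unclassifiable IIP | Kept |
| IPF code and J84.9 on the index date | Multiple | Kept |
| IPF code (ICD-10 J84.1) on the index date, RA code in the lookback | RA-ILD | Kept |
| IPF code on the index date, HP code in the lookback | Hypersensitive pneumonitis | Kept |

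So exclusion 1 removes some patients with an IPF code but not all, and a nintedanib claim changes none of these results.

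**4. Other removal.** A prior user still leaves the cohort if another proxy is met at baseline, such as three CTs or three lung function tests within 365 days, home oxygen or a respiratory hospitalisation.

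**5. Size.** The plan gives no figure to reproduce. Let f be the share of prior users left in the cohort, p1 their progression risk and p0 the risk in the rest. As a simple mixture, ignoring censoring:

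shift = f × (p1 − p0)

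All three inputs are assumptions. Take p0 = 30% or 50% and p1 = 70% or 95%. The smallest difference is 70 − 50 = 20 points and the largest is 95 − 30 = 65 points.

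| f | Smallest shift (points) | Largest shift (points) |
|---|---|---|
| 0.5% | 0.005 × 20 = 0.1 | 0.005 × 65 = 0.325 |
| 1% | 0.2 | 0.65 |
| 3% | 0.6 | 1.95 |
| 5% | 1.0 | 3.25 |
| 10% | 2.0 | 6.5 |

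If remaining users progress less often, say p1 = 30% against p0 = 50%, the shift is 0.005 × (−20) = −0.1 points at f = 0.5% and 0.10 × (−20) = −2.0 points at f = 10%.

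**The case against.** The strongest reply is that the date limit is deliberate and reasoned. Under the written definition, a patient with a pre-approval claim has not met the progression criteria, so admitting that patient follows the plan. This stands. A reader might infer that the two exclusions were meant to remove these patients and that the plan contradicts itself; the text does not say so.

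Second, no document shows that such patients remain. Those with active disease are the most likely to be removed by another baseline proxy, and those who stay may be light users of care, so even the sign of p1 − p0 is open. This also stands.

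Third, the documents never state that nintedanib was approved for IPF, or when. They support only the absence of a named non-IPF indication, so treatment as IPF is a plausible reading of a claim and not a demonstrated one.

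Fourth, the planned tables will show 6-month users by progression status and subgroup. That helps a reader judge prevalence, but it covers half of the 12-month baseline and gives no Kaplan-Meier estimate without these patients. The optional analysis with modified progression criteria in Section 9.7.4 is not a commitment and does not mention baseline drug use.

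Finally, making baseline nintedanib an exclusion criterion would be hard to defend. It would drop real-world users from a study whose secondary objective describes treatment, and it would empty a planned row of Table 2. If identification also moves with the later cut-off, which Section 9.7.4 does not settle, it could remove SSc-ILD patients treated after that approval. This is why the remedy below is a sensitivity analysis.

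**Conclusion.** The gap is real but limited. In the main analysis, a baseline nintedanib claim on its own triggers neither exclusion, and no committed analysis shows whether this matters. The primary risk set can therefore contain prior users who count as non-IPF and not yet progressed.

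It would go too far to conclude that the cohort does contain them, that they have IPF or had already progressed, or that the incidence is overestimated. Under the assumed values the overall shift runs from 0.1 to 6.5 points upward, or from 0.1 to 2.0 points downward in the reverse case shown. A larger effect in a particular subgroup is possible but has no support in the documents. The date argument covers analyses ending on 28-May-2020; with a later cut-off, some baseline claims could follow a named approval. This is an inexpensive improvement and does not invalidate the design.

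**What to change.** 1. Leave the main cohort as it is, and keep the rule that nintedanib claims before 29-May-2020 are not events.
2. Add to Section 9.7.4, as a commitment, a repeat of the primary outcome (overall and in the three subgroup patterns) without patients who have any nintedanib claim in the 12 months up to and including the index date. Report how many are removed in total and in each subgroup.
3. In the analysis to the latest cut-off, apply to the nintedanib row, for follow-up events, the new-claim condition already used for the other drugs: no nintedanib in the 12 months before index. A prior user's refill then does not count as new progression.

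The cost is one paragraph, one filter, one more run and a slightly smaller cohort in that run. The nintedanib lookback must be 12 months where Table 2 extracts 6, but the new-claim rules for immunosuppressants and corticosteroids already need a 12-month drug history.
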